4.4.3 CYP Interactions

At the systemic exposure levels expected in this study, acalabrutinib inhibition of CYP metabolism is not anticipated. However, acalabrutinib is metabolized by CYP3A. Participants who are known to require the concomitant administration of strong inhibitors or inducers of CYP3A4 at the time of study entry are excluded from trial participation. The concomitant use of strong or moderate inhibitors of CYP3A4, or strong inducers of CYP3A4, should be avoided when possible while the participant is receiving treatment with acalabrutinib. If it is medically necessary to administer while on study, monitor the participant closely for potential toxicities and refer to dose adjustment table below.

Table 8: Acalabrutinib Dose Adjustments for Concomitant Administration of CYP Agents¹

CYP3A	Co-Administered Drug	Recommended Acalabrutinib Adjustment
Inhibition	Strong CYP3A4 Inhibitor	Avoid concomitant use when possible. If used short-term (e.g. anti-infectives for up to 7 days), hold dosing of acalabrutinib.
Inhibition	Moderate CYP3A4 Inhibitor	100 mg once daily.
Induction	Strong CYP3A4 Inducer	Avoid concomitant use when possible. If these inducers cannot be avoided, increase dose to 200 mg twice daily.
1. To be made in accordance with institutional standards of practice, treating investigator judgement, and FDA prescribing information.		

The *in vitro* ability of umbralisib acting as a substrate, inhibitor, or inducer of cytochrome P450 enzymes (CYPs), conjugating enzymes, and transporters was evaluated as per FDA Guidance. Except for a P-gp inhibitory potential, the results demonstrated no drug-drug interaction effects against major CYPs, conjugating enzymes, and transporters evaluated.

Ublituximab is a protein and is expected to be metabolically degraded through peptide hydrolysis. Based on this expectation, ublituximab is an unlikely candidate for cytochrome P450-mediated drug-drug interactions.

4.4.4 Agents that Reduce Gastric Acidity

The effect of agents that reduce gastric acidity (e.g., proton pump inhibitors or antacids) on acalabrutinib absorption was evaluated in a healthy volunteer study. Results from this study indicate that subjects should avoid the use of calcium carbonate containing drugs or supplements for a period of at least 2 hours before and at least 2 hours after taking acalabrutinib. Use of omeprazole, esomeprazole, lansoprazole or any other proton pump inhibitors while taking acalabrutinib is not recommended due to a potential decrease in study drug exposure. However, the decision to treat with proton-pump inhibitors during the study is at the treating investigator's discretion, with an understanding of the potential benefit to the subject's gastrointestinal condition and a potential risk of decreased exposure to acalabrutinib.

Although the effect of H2-receptor antagonists (such as famotidine or ranitidine) on acalabrutinib absorption has not been evaluated, if treatment with an H2-receptor antagonist is required, the H2-receptor antagonist should be taken approximately 2 hours after an acalabrutinib dose.

4.4.5 Acceptable Forms of Contraception and Pregnancy Guidelines

4.4.5.1 Definition of Females Not of Childbearing Potential

Females are considered post-menopausal and not of child bearing potential if they have had 12 months of natural (spontaneous) amenorrhea with an appropriate clinical profile (e.g. age appropriate, history of vasomotor symptoms) or six months of spontaneous amenorrhea with serum FSH levels > 40 mIU/mL and estradiol < 20 pg/mL or have had surgical bilateral oophorectomy (with or without hysterectomy) at least six weeks ago. In the case of oophorectomy alone, only when the reproductive status of the woman has been confirmed by follow up hormone level assessment is she considered not of child bearing potential.

4.4.5.2 Fertile Males

Fertile males, defined as all males physiologically capable of conceiving offspring, must use a condom during treatment and for 4 months after the last dose of study treatment. They should also not father a child during this period.

4.4.5.3 Pregnancies

To ensure patient safety, each pregnancy in a patient on study treatment must be reported and followed as per the guidelines in **Section 7**.

4.4.5.4 Acceptable Contraception

Highly effective methods of contraception (to be used during heterosexual activity) are defined as methods that can achieve a failure rate of $<1\%$ per year when used consistently and correctly.

Such methods include:

- Combined (estrogen and progestogen containing) hormonal contraception associated with inhibition of ovulation, which may be oral, intravaginal, or transdermal
- Progestogen-only hormonal contraception associated with inhibition of ovulation, which may be oral, injectable, or implantable
- Intrauterine device (IUD) or intrauterine hormone-releasing system (IUS)
- Bilateral tubal occlusion
- Vasectomy (with medical assessment and confirmation of vasectomy surgical success)
- Sexual abstinence (only if refraining from heterosexual intercourse during the entire period of risk associated with the study treatments)

Hormonal contraception may be susceptible to interaction with study or other drugs, which may reduce the efficacy of the contraception method.

Abstinence (relative to heterosexual activity) can only be used as the sole method of contraception if it is consistently employed during the entire period of risk associated with the study treatments as the subject's preferred and usual lifestyle. Periodic abstinence (e.g., calendar, ovulation, sympto-thermal, and post-ovulation methods) and withdrawal are not acceptable methods of contraception.

If a contraceptive method is restricted by local regulations/guidelines, then it does not qualify as an acceptable highly effective method of contraception for subjects participating at sites in the relevant region.

The following are **unacceptable** forms of contraception for females of childbearing potential:

- Female condom
- Natural family planning (rhythm method) or breastfeeding
- Fertility awareness
- Withdrawal
- Cervical shield

4.4.6 Live Virus Vaccines

Live virus vaccines are prohibited beginning 4 weeks prior to the first dose of ublituximab and for the duration of ublituximab treatment.

4.5 Criteria for Taking a Participant Off Protocol Therapy

Duration of therapy will depend on individual response, evidence of disease progression and tolerance. In the absence of treatment delays due to adverse event(s), treatment may continue for a maximum of 24 cycles or until one of the following criteria applies:

- Disease progression, with the exception of participants who relapse following confirmed CR and treatment discontinuation who are permitted to be re-treated as described in **Section 5.1**
- Intercurrent illness that prevents further administration of treatment
- Unacceptable adverse event(s)
- Participant becomes pregnant or plans to become pregnant
- Participant demonstrates an inability or unwillingness to comply with the oral medication regimen and/or documentation requirements
- Participant decides to withdraw from the protocol therapy
- General or specific changes in the participant's condition render the participant unacceptable for further treatment in the judgment of the treating investigator

Participants will be removed from the protocol therapy when any of these criteria apply. The reason for removal from protocol therapy, and the date the participant was removed, must be documented in the case report form (CRF). Alternative care options will be discussed with the participant.

When a participant is removed from protocol therapy and/or is off of the study, the participant's status must be updated in OnCore in accordance with [REGIST-OP-1](#).

4.6 Duration of Follow Up

Participants will be followed for 30 days after removal from protocol therapy or until death, whichever occurs first, for adverse events. Participants removed from protocol therapy for unacceptable adverse event(s) will be followed until resolution or stabilization of the adverse event. Following the 30 day follow up period, participants will be followed for a maximum of 5 years after treatment discontinuation to observe treatment response and survival status.

4.7 Criteria for Taking a Participant Off Study

Participants will be removed from study when any of the following criteria apply:

- Completion of the 5 year follow-up period
- Lost to follow-up
- Withdrawal of consent for data submission
- Death

The reason for taking a participant off study, and the date the participant was removed, must be documented in the case report form (CRF). In addition, the study team will ensure the participant's status is updated in OnCore in accordance with [REGIST-OP-1](#).

5. DOSING DELAYS/DOSE MODIFICATIONS

Dose delays and modifications will be made as indicated in the following table(s). The descriptions and grading scales found in the revised NCI Common Terminology Criteria for Adverse Events (CTCAE) version 5.0 will be utilized for dose delays and dose modifications of non-hematologic toxicity. A copy of the CTCAE version 5.0 can be downloaded from the CTEP website

http://ctep.cancer.gov/protocolDevelopment/electronic_applications/ctc.htm. The iwCLL 2018 criteria will be used for grading and assessment of hematologic toxicity (**Appendix E**).¹

5.1 Dose Delays

Umbralisib may be held for a maximum of 56 days to allow for recovery of toxicity, and acalabrutinib may be held for a maximum of 28 days. Ublituximab may be delayed for a maximum of 2 cycles (56 days). Participants requiring a longer delay should be removed from

protocol therapy. Participants who are deriving clinical benefit who require a longer hold of any of the study agents may be allowed to continue treatment following discussion and agreement with the sponsor-investigator.

If attribution of the toxicity is known, study medications may be held independently of each other. For example, a participant may continue dosing with acalabrutinib and umbralisib while holding ublituximab at the treating investigator's discretion. If attribution of the toxicity is unknown or the combination of study agents may be contributing to the toxicity, all study agents must be held. Refer to **Section 6.3** for toxicity management guidelines.

In the event of a dose hold due to toxicity, the counting of cycle days and protocol assessment schedule will continue without interruption. For example, a participant who holds dosing of umbralisib and acalabrutinib on Cycle 4 Day 15 to Cycle 4 Day 18 for toxicity will resume dosing on Cycle 4 Day 19 and proceed with their next scheduled clinic visit as previously planned (Cycle 5 Day 1). Interim visits may be conducted as clinically necessary to manage toxicity; however, the cycle will not restart and doses will not be "made up" in the event of dosing delays.

5.2 Dose Modifications

Permitted dose reductions of acalabrutinib and umbralisib are detailed below. Once a participant's dose has been reduced due to toxicity, it may not be re-escalated. If a subject requires a dose reduction of umbralisib and further evaluation of the toxicity reveals the event was not related to umbralisib, this should be recorded in the medical record and dose re-escalation to the previous umbralisib dose may be considered at the discretion of the treating investigator after consultation with the sponsor-investigator. No dose reductions of ublituximab are permitted. If the participant cannot tolerate the dose of ublituximab, ublituximab should be discontinued.

If attribution of the toxicity is known, dose reductions may occur independently of each other. For example, the dose of umbralisib may be reduced while maintaining the dose of acalabrutinib. If toxicity attribution is unknown or the combination of study agents may contribute to the toxicity, both agents must be dose reduced.

Table 9: Umbralisib Dose Reductions	
Dose Reduction Level	Umbralisib Dose (Once Daily)
-1	600 mg
-2	400 mg
-3	Discontinue

Table 10: Acalabrutinib Dose Reductions ^{1,2}	
Dose Reduction Level	Acalabrutinib Dose
-1	100 mg once daily
-2	Discontinue
1. Dose modifications of acalabrutinib may be made in	

Table 10: Acalabrutinib Dose Reductions ^{1,2}	
Dose Reduction Level	Acalabrutinib Dose
accordance with the FDA prescribing information. 2. Refer to Section 5.4 for dose modifications for co-administered CYP3A drugs.	

If attribution of the toxicity is known, discontinuation of study medications may also occur independently of each other with agreement from the sponsor-investigator. For example, participants who cannot tolerate ublituximab may be allowed to continue to receive umbralisib and acalabrutinib if the sponsor-investigator provides approval.

5.3 Toxicity Management

Management of toxicity considered at least possibly related to the study agents is detailed in the tables below.

Table 11: Hematologic Toxicity Management ¹		
Event Term	Grade	Study Agent Management Guidelines ²
Neutrophil count decreased	Grade 3	
Provide supportive care as warranted.
 
Maintain current dose of umbralisib and acalabrutinib.
 
For recurrent or persistent Grade 3 neutropenia unresponsive to supportive care, reduce umbralisib by one dose level.
 
Maintain full dose and schedule of ublituximab, if applicable.

Neutrophil count decreased	Grade 4	
Provide supportive care as warranted. Hold dosing of study agents until resolution to \leq Grade 3.
 
First and second occurrence: resume umbralisib and acalabrutinib at the same dose level.
 
Recurrence after second re-challenge: resume umbralisib and acalabrutinib with one dose level reduction.
 
If applicable, resume ublituximab at full dose and schedule.

Febrile neutropenia	\geq Grade 3	
Provide supportive care as warranted. Hold study agents until resolution.
 
First occurrence: resume umbralisib and acalabrutinib at the same dose level.
 
Recurrence after re-challenge despite supportive care: reduce dose of umbralisib by one dose level.
 
If applicable, resume ublituximab at full dose and schedule upon resolution.

Table 11: Hematologic Toxicity Management¹		
Event Term	Grade	Study Agent Management Guidelines²
Platelet count decreased ³	Grade 3 with clinically significant bleeding -OR- Grade 4	
Provide supportive care as warranted.
 
First occurrence: delay umbralisib and acalabrutinib until Grade ≤ 3 without clinically significant bleeding; thereafter, resume umbralisib and acalabrutinib at the same dose level.
 
Second occurrence: delay umbralisib and acalabrutinib until Grade ≤ 3 without clinically significant bleeding; thereafter, resume umbralisib and acalabrutinib at next lower dose level unless there is a clear alternative explanation for the event.
 
Delay ublituximab until Grade ≤ 3 without clinically significant bleeding; thereafter, resume ublituximab at full dose and schedule.

1. Grading of hematologic toxicity will be per iwCLL 2018 criteria (**Appendix E**).¹
 2. Management of acalabrutinib may be made in accordance with the FDA prescribing information.
 3. If participant receives a platelet transfusion, they will be considered to have grade 4 toxicity for that day and the next 2 calendar days regardless of actual platelet count.

Table 12: Non-Hematologic Toxicity Management		
Event Terms	CTCAE Grade	Study Agent Management Guidelines¹
Pulmonary & Related Infections ²	Grade 3	
Provide supportive care as warranted.
 
Maintain acalabrutinib dosing. Hold dosing of umbralisib and ublituximab (if applicable) until complete resolution. Acalabrutinib may also be held at the treating investigator's discretion and SHOULD be held for any suspected fungal or opportunistic infections until resolution of infection to grade 1 or less. Resume acalabrutinib at the same dose level.
 
If suspicious for a possible drug-related pneumonitis, resume umbralisib at next lower dose level. If recurrence after re-challenge, permanently discontinue umbralisib.
 
Upon complete resolution, resume ublituximab at full dose and schedule. If recurrence after re-challenge, permanently discontinue ublituximab.

Pulmonary & Related Infections ²	Grade 4	
Provide supportive care as warranted.
 
Permanently discontinue umbralisib and ublituximab (if applicable).

Table 12: Non-Hematologic Toxicity Management

Event Terms	CTCAE Grade	Study Agent Management Guidelines ¹
Colitis	ANY	
Provide supportive care as warranted. Hold dosing of umbralisib and ublituximab (if applicable) until resolution. Acalabrutinib may also be held at the treating investigator's discretion.
 
Upon resolution, resume umbralisib at the next lower dose level. Acalabrutinib may be resumed at the same dose level or reduced at the treating investigator's discretion. Resume ublituximab at the same dose and schedule.

Liver Toxicity Includes: ALT (SGPT), AST (SGOT), Bilirubin increased	Grade 1	
Maintain current dose and schedule of umbralisib, acalabrutinib, and ublituximab (if applicable).
 
Assess concomitant medications and risk factors.³ Monitor liver function laboratories every 1 – 2 weeks until resolution to baseline.

Liver Toxicity Includes: ALT (SGPT), AST (SGOT), Bilirubin increased	Grade 2	
Assess concomitant medications and risk factors.³
 
First Occurrence: Maintain current dose and schedule of umbralisib, acalabrutinib, and ublituximab (if applicable).
 
Begin supportive care (prednisone 0.5 – 1.0 mg/kg/day or equivalent per treating investigator's discretion).⁴
 
Monitor liver function laboratories at least weekly until Grade 1 or baseline. Once resolved to Grade 1 or baseline, taper prednisone by 10 mg per week until off.
 
If liver toxicity recurs:
 
 • Re-initiate steroids. • Delay umbralisib and ublituximab dosing. • Monitor liver function labs at least weekly until resolution to Grade 1 or baseline. • Once resolved to Grade 1 or baseline, restart umbralisib at current dose and resume ublituximab at full dose and schedule. • Taper prednisone by 10 mg per week until off.

Table 12: Non-Hematologic Toxicity Management		
Event Terms	CTCAE Grade	Study Agent Management Guidelines ¹
Liver Toxicity Includes: ALT (SGPT), AST (SGOT), Bilirubin increased	Grade ≥ 3	
Assess concomitant medications and risk factors.³
 
Hold dosing of umbralisib, ublituximab, and acalabrutinib.
 
Begin supportive care (prednisone 0.5 – 1.0 mg/kg/day or equivalent per treating investigator's discretion).⁴
 
Monitor liver function labs at least weekly until Grade 1 or resolution to baseline. Once resolved to Grade 1 or baseline, resume dosing with study agents, beginning with acalabrutinib and adding umbralisib and ublituximab (as applicable) one week later if the liver toxicity does not return upon re-introduction of acalabrutinib. Reduce dose of umbralisib by one dose level, resume full dose and schedule of acalabrutinib and ublituximab. Taper prednisone by 10 mg per week until off.

Any other non-hematologic toxicity	\leq Grade 2	
No change in study agent dosing or schedule.⁵ Implement supportive care as appropriate.
 
NOTE: If persistent grade 2 diarrhea despite supportive care, delay umbralisib until \leq grade 1; thereafter, resume umbralisib at next lower dose level.

Table 12: Non-Hematologic Toxicity Management		
Event Terms	CTCAE Grade	Study Agent Management Guidelines ¹
Any other non-hematologic toxicity	≥ Grade 3	
Implement supportive care as appropriate.
 
First occurrence: hold dosing of study agents until resolution to ≤ Grade 2 or baseline. Upon resolution, may resume dosing with umbralisib and acalabrutinib at the same dose level, or at the treating investigator's discretion, may reduce dose by one dose level. Resume ublituximab at the full dose and schedule.
 
Recurrence: hold dosing of study agents until resolution to ≤ Grade 2 or baseline. Upon resolution, resume dosing with umbralisib and acalabrutinib with one dose level reduction. Resume ublituximab at the full dose and schedule.
 
Exceptions:
 
 Asymptomatic laboratory abnormalities considered non-clinically significant: participants may continue dosing at the treating investigator's discretion. Asymptomatic laboratory abnormalities that resolve to ≤ Grade 2 or baseline within 48 hours of repletion or treatment: study medication should be held until resolution to Grade 2 and may be resumed at the same dose level or with one dose level reduction at the treating investigator's discretion. Treatment and resumption of study medication dosing may occur on the same day.
		
 Management of acalabrutinib may be made in accordance with the FDA prescribing information. For sinopulmonary infections clearly not related to immune-mediated pneumonitis, umbralisib may be continued at the treating investigator's discretion. While pneumonitis has been minimal with umbralisib, it is a reported adverse event associated with other PI3K delta inhibitors. Use of anti-pneumocystis and anti-herpetic viral prophylaxis is required prior to the start of therapy, refer to Section 5.4. Assess for disorders of lipids and glucose, thyroid disorders, alcohol use, viral infections, etc. Supportive Care may include aggressive management of lipid, glucose, other metabolic disorders, viral infections, etc. Important: Before initiating steroids, check for viral hepatitis or CMV infection. At the treating investigator's discretion, dosing of the study agent(s) may be held and/or dose reduced for intolerable Grade 2 toxicity.

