6.3 Serious Adverse Event Reporting

A serious adverse event (SAE) is any adverse event that occurs after the initial dose of study treatment, during treatment, or within 30 days of the last dose of treatment that results in one of the following outcomes or meets at least one of the following criteria:

- Death
- Hospitalization for greater than 24 hours
- Prolonging an existing inpatient hospitalization
- A life-threatening experience (that is, immediate risk of dying)
- Persistent or significant disability/incapacity
- Congenital anomaly/birth defect
- Any suspected transmission of an infectious agent via a study agent (e.g. Prion Protein Transmitting Transmissible Spongiform Encephalopathy)
- Any confirmed occurrence of Hy's Law, defined as an ALT or AST $\geq 3 \times$ institutional ULN **AND** concurrent total bilirubin $\geq 2 \times$ institutional ULN without findings of cholestasis
- Considered significant by the investigator for any other reason

If an investigator becomes aware of an SAE that is considered related to acalabrutinib after completion of the 30-day period following the last dose of acalabrutinib, the event should also be reported as an SAE to Acerta Pharma at the contact information given below.

Previously planned (prior to signing the informed consent form) surgeries, and non-disease related elective surgeries planned during the course of the study, should not be reported as SAEs unless the underlying medical condition has worsened or appeared during the course of the study. Events that occur prior to the first administration of study medication should not be reported as SAEs.

Preplanned hospitalizations or procedures for pre-existing conditions that are already recorded in the patient's medical history at the time of study enrollment should not be considered SAEs. Hospitalization or prolongation of hospitalization without a precipitating clinical AE (e.g., for the administration of study therapy or other protocol-required procedure) should not be considered SAEs.

Important medical events that may not result in death, be life-threatening, or require hospitalization may be considered SAEs when, based on appropriate medical judgment, they may jeopardize the patient and may require medical or surgical intervention to prevent one of the outcomes listed in this definition.

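### Table 12 has no line for a concurrent ALT/AST and bilirubin rise, so a Hy's Law event below Grade 3 falls in a Grade 2 row that never directs an acalabrutinib hold

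*Combined protocol and SAP*

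**What the plan says.** Section 5.3 sets the scope of its tables: "Management of toxicity considered at least possibly related to the study agents is detailed in the tables below". Within Table 12, the liver rows cover ALT, AST and bilirubin as one category, split into Grade 1, Grade 2 and Grade 3 or higher.

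- **Grade 1:** all agents continue, with liver tests every 1 to 2 weeks.
- **Grade 2, first event:** "First Occurrence: Maintain current dose and schedule of umbralisib, acalabrutinib, and ublituximab (if applicable". Prednisone is started and liver tests are done at least weekly.
- **Grade 2, recurrence:** steroids restart and sites are told "Delay umbralisib and ublituximab dosing". Acalabrutinib is not named.
- **Grade 3 or higher:** "Hold dosing of umbralisib, ublituximab, and acalabrutinib". Once the event is back to Grade 1 or baseline, acalabrutinib restarts first; the other two follow a week later if liver toxicity has not returned.

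Section 6.3 separately lists as a serious adverse event "Any confirmed occurrence of Hy's Law, defined as an ALT or AST" of at least 3 x ULN with concurrent total bilirubin of at least 2 x ULN and no cholestasis. It attaches no dosing action. Section 5.5 records that umbralisib and ublituximab are no longer supplied as of March 2023 and that participants still on treatment may continue acalabrutinib.

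**The concern.** Section 6.3 singles out the combination of raised transaminases and raised bilirubin as serious, even where neither value would be severe alone. Table 12 does not recognise the combination. It grades each test, so the combined event gets the same dosing instruction as an isolated Grade 2 enzyme rise: keep giving everything.

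The gap is plainest for a participant on acalabrutinib alone. The only delay in the Grade 2 row names two drugs that person no longer receives, so the row directs no hold however often the event recurs.

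What is at stake is continued dosing through a possible drug-related liver injury. Table 13 lists no hepatic event as expected for acalabrutinib. Section 4.4.2 does warn of viral hepatitis reactivation with it, and section 2.4.1.2 reports one case of liver failure and death after hepatitis B reactivation across its development program, which included combinations.

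**Working it through.** The plan states no figure on this point, so there is none to reproduce. The check is whether an event can meet section 6.3 and still be graded below 3, and what each text then directs.

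**Inputs**

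- Hy's Law thresholds (section 6.3): ALT or AST at least 3 x ULN, bilirubin at least 2 x ULN.
- Grading scale (section 5): CTCAE v5.0. Its liver cut-points are not printed. *Assumed*, for a normal baseline: ALT/AST Grade 2 above 3 and up to 5 x ULN, Grade 3 above 5 x; bilirubin Grade 2 above 1.5 and up to 3 x ULN, Grade 3 above 3 x. The higher of the two grades is taken to select the row.
- Doses (section 4.1): acalabrutinib 100 mg twice daily, umbralisib 800 mg once daily.

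**Step 1: overlap.** Meeting 6.3 while staying below Grade 3 requires 3 ≤ ALT/AST ≤ 5 and 2 ≤ bilirubin ≤ 3 (all x ULN). The region is not empty.

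| ALT/AST (x ULN) | Bilirubin (x ULN) | Grades | Row that applies |
|---|---|---|---|
| 3.0 | 2.0 | 1 and 2 | Grade 2: maintain |
| 3.5 | 2.5 | 2 and 2 | Grade 2: maintain |
| 5.0 | 3.0 | 2 and 2 | Grade 2: maintain |
| 5.1 | 2.5 | 3 and 2 | Grade 3 or higher: hold all |
| 4.0 | 3.1 | 2 and 3 | Grade 3 or higher: hold all |

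**Step 2: sensitivity to the assumed cut-points.** Trying Grade 3 bounds of 2.5, 3, 4, 5 and 6 x ULN for ALT/AST against 1.5, 2, 2.5 and 3 x for bilirubin, the region exists whenever the bounds are at least 3 x and 2 x respectively. It is empty if either is lower.

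**Step 3: abnormal baseline.** If grades are taken relative to an abnormal baseline (also assumed), the region widens. With ALT at the usual entry limit of 2.5 x ULN (section 2.7.8), values up to 5 × 2.5 = 12.5 x ULN stay below Grade 3.

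**Step 4: what other text directs for this event.**

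- Section 4.4.2: a rise in liver enzymes in a participant with prior hepatitis B holds ublituximab at once; acalabrutinib is not named at that step. Detectable HBV DNA stops all study drugs, but the trigger is the virus, not the liver-test pattern.
- Section 6.3 reporting: the sponsor-investigator is told within 1 business day; no dosing step follows.
- Section 4.5: removal for unacceptable adverse events or a changed condition, by judgement.
- Table 12 footnote 1: acalabrutinib may be managed under its label, which is not among the documents.
- Table 12 footnote 5: "dosing of the study agent(s) may be held and/or dose reduced for intolerable Grade 2 toxicity", but it is marked on the row for other non-hematologic toxicity at Grade 2 or below, not on the liver rows.

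None directs an acalabrutinib hold on the Hy's Law criteria.

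**Step 5: exposure under 'maintain'.** Between weekly liver tests at full dose: acalabrutinib 2 × 7 = 14 doses, 14 × 100 = 1,400 mg. During combination therapy, umbralisib adds 7 × 800 = 5,600 mg, plus ublituximab if due. This restates the regimen; it is not a measure of harm.

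**The case against.** **A conflict with section 5.1.** A reader might infer that Table 12 contradicts section 5.1, which says that if attribution is unknown or "the combination of study agents may be contributing to the toxicity, all study agents must be held". The documents do not support that. The sentence contrasts holding agents separately when attribution is known with holding them together when it is not, and then refers the reader to the toxicity guidance. It is best read as saying which agents to hold once a hold is needed. Otherwise it would override every row that continues dosing, including Grade 3 neutropenia and Grade 1 liver events. No direct conflict is claimed.

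**Acalabrutinib cannot be held.** A reader might also infer that the protocol forbids holding acalabrutinib at Grade 2. It does not. Section 5.1 allows agents to be held separately when attribution is known. Footnote 1 sits on the management column and so reaches the liver rows, and section 4.5 leaves room for clinical judgement. This stands, and it narrows the point to the absence of a directed hold.

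**The risk is already watched.** The Grade 2 row requires risk-factor review and at least weekly liver tests, and a footnote requires a check for viral hepatitis or CMV before steroids. Section 4.4.2 adds monthly HBV DNA testing for participants positive for core antibody with negative DNA. These safeguards reduce the risk materially but do not change the instruction to maintain.

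**Serious does not mean hold.** Section 6.3 attaches no dosing action to any of its criteria, so seriousness alone does not oblige a hold. That is right. The argument for one here is that Table 12 already holds all agents for more marked liver toxicity and overlooks this combination.

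**Conclusion.** The point holds as a low-magnitude safety improvement. The absence of a combined-rise line, and of any acalabrutinib hold in the Grade 2 row, can be read directly from Table 12. That a Hy's Law event can land in the Grade 2 row rests on the assumed CTCAE cut-points, under which the affected region is ALT/AST 3 to 5 x ULN with bilirubin 2 to 3 x ULN from a normal baseline. Events reaching Grade 3 on either test are already held, and that row is not at fault.

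The number affected is unknown and probably small: the documents give no rate of combined elevation and no count of participants on acalabrutinib alone. With umbralisib and ublituximab withdrawn, an amendment can now help only participants still taking acalabrutinib. No sample size, error rate or efficacy analysis is affected.

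**What to change.** Add one footnote to the Table 12 liver rows: a confirmed event meeting the section 6.3 Hy's Law definition is managed under the Grade 3 or higher liver row whatever the individual grades, unless it is explained by Gilbert's disease, hemolysis or liver involvement present at baseline. All agents being given are held, including acalabrutinib alone; the cause is assessed; restart follows that row's existing rule. The exception is needed because section 2.7.8 admits such participants with bilirubin up to 3 x ULN (Gilbert's disease or hemolysis) or ALT/AST up to 5 x ULN (hemolysis or liver involvement).

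If sponsor-investigator agreement to restart is wanted, apply it to Hy's Law events of every grade. Otherwise a milder event would face a stricter restart rule than a worse one.

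The cost is a footnote in an amendment. No new tests are needed, since bilirubin, AST and ALT are already in the serum chemistry panel. The downside is an occasional extra hold. Section 5.1 says "acalabrutinib may be held for a maximum of 28 days", which is 28 / 7 = 4 weekly liver checks; continuing after a longer hold needs sponsor-investigator agreement.
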